PROTOCOL TITLE: Use of NPH versus Basal Bolus Insulin for Steroid Induced Hyperglycemia

PRINCIPAL INVESTIGATOR:

[name]. Division of Endocrinology, Metabolism and Molecular Medicine Department of Medicine Northwestern University Feinberg School of Medicine [name] [contact] [contact]

VERSION NUMBER:

Version Number 1

VERSION DATE:

2/19/2018

Co-Principal Investigator

[name]., Division of Endocrinology, Metabolism and Molecular Medicine

Fellow Investigator

[name]., Division of Endocrinology, Metabolism and Molecular Medicine

Co-Investigators:

[name], MSN, APRN, Glucose Management Service

[name], APRN, Glucose Management Service

Study Site:

Northwestern Memorial Hospital

Study identifiers:

STU00207079, NCT03511521

OBJECTIVES:

- 1.) To determine which insulin regimen, NPH in addition to basal/bolus insulin or just basal/bolus insulin, provides better glycemic control in patients on once daily dosing of steroids
- 2.) Determine which dosing regimen leads to less adverse events, specifically hypoglycemia

BACKGROUND:

Glucocorticoids are known to cause an increase in insulin resistance, leading to hyperglycemia, in both diabetic and non-diabetic patients. In both the inpatient and outpatient setting, steroids are used for their anti-inflammatory property to treat a variety of conditions. There is a paucity of information regarding the best way to treat steroid-induced hyperglycemia. Generally insulin is administered in the hospital using a basal/bolus approach, i.e. giving a long-acting insulin such as glargine to control hepatic glucose production overnight and between meals and giving a short-acting insulin as a bolus before meals to control the postprandial rise in glucose. Approaches that have been used to adjust for the additional hyperglycemia induced by high dose steroids, which are usually administered once daily in the morning, include the addition or substitution of NPH insulin for glargine insulin vs. adjusting the basal/bolus regimen.

In 2008, Bevier et al investigated increasing doses of total daily insulin needed in Type I diabetic patients on an insulin pump who were administered a fixed dose of steroids for three days. The study noted an increase in basal rates and insulin boluses required after six hours following the first dose of prednisone due to rising insulin resistance. The study concluded that insulin doses should be increased by at least 30% when the corticosteroid therapy is started but may need to be increased by up to 70% or more to normalize blood glucose levels⁴. While it is known that steroids cause an increase in insulin resistance and an increased total daily dose of insulin requirements; the best way to administer this insulin is still unknown.

While some studies have looked at using NPH versus glargine as basal insulin for steroid-induced hyperglycemia^{1,2,3}, few studies have looked at the addition of NPH to a basal bolus regimen for treating steroid-induced hyperglycemia.

A pilot study done at the University of Colorado looked into the use of NPH plus basal bolus insulin versus just basal bolus insulin doses to treat steroid induced hyperglycemia, specifically in cystic fibrosis related diabetes patients receiving methylprednisolone.⁵ Similar to Beiver et al⁴, they concluded that with the addition of steroids, there was an overall increase of total daily doses of insulin by 40%; half of the arm received this increase in the form of NPH in addition to glargine and lispro while half of them received this in the form of an increase in the glargine and lispro doses. The study showed that methylprednisolone raised prelunch and predinner glucose levels in patients treated with glargine/lispro alone; however, the addition of NPH with methylprednisolone significantly decreased the rise in postprandial glucose at lunch and dinner compared to the glargine/lispro group but still did not return the glucose levels to acceptable levels.⁵

Our study aims to further study the use of NPH in addition to glargine and lispro in the setting of steroid use to achieve improved glycemic control in the inpatient setting.

References:

Our study aims to recruit 25 inpatients at Northwestern Memorial Hospital to each study arm. Eligible patients will be those who are receiving once daily dosing of prednisone or methylprednisolone for any medical condition. Examples include patients being treated with steroids for respiratory issues, stem cell transplant patients, and cystic fibrosis related diabetes patients. This will be a prospective, randomized control study in which each patient will be randomized to one of two arms. Consent will be obtained at the initial day of an Endocrine or Glucose Management Service (GMS) inpatient consult, and then subsequently randomized.

Study Intervention

One group will receive NPH in addition to their current glargine lispro basal/bolus regimen at the time of the prednisone administration. Another group will continue to receive glargine and lispro; however, their basal and bolus regimens will be increased (see attached tables for details).

DATA AND SPECIMEN BANKING:

Data will be stored both in a locked cabinet and password protected computer and deidentified data will be stored on endocrine FSM research server (R Drive) where only study personnel will have access. Only the investigators in the study will have access to the data.

Data will be stored until final analyses and all publications have been completed and will then be destroyed by erasing any stored files on the computer and any printed out data.

There will be no specimen banking.

DATA AND SPECIMEN MANAGEMENT:

An analysis of the routine finger stick capillary blood glucose levels will be done (see below). No extra fingersticks will be carried out just for the study. Glycemic control will be assessed by measuring the mean of the 4 glucose levels (premeal and bedtime) for the first 3 days of treatment and comparing these means between the groups. A secondary analysis will be to compare the proportions of values in

the therapeutic targets of 80 – 140 mg/dL and 80 – 180 mg/dL. An additional analysis will compare the proportion of values < 70 mg/dL, the threshold value for hypoglycemia.

In the study by Seggelke et al (5), the 3 day means of 3 daily premeal glucose levels for the two groups (basal/bolus alone vs. basal/bolus + NPH) were 241 and 176 mg/dL (a difference of 65 mg/dL) with standard deviations of 36 and 28 mg/dL for the two groups. If we assume that our modified basal/bolus regimen gives improved glycemic results comparable to theirs, we have assumed the following for our statistical power calculations: a standard deviation of 30 mg/dL and assume half the difference in the means of about 30 mg/dL, which can be considered to be clinically significant, then a sample size of 20 in each group would have statistical (two-tailed) power of 0.869 to demonstrate this difference between the groups of 30 mg/dL using an alpha=0.05. We plan to recruit 25 in each group to allow for drop-outs, because some patients may not stay on methylprednisolone/prednisone for 3 days.

PROVISIONS TO MONITOR THE DATA TO ENSURE THE SAFETY OF PARTICIPANTS:

There is always a risk of both hyperglycemia and hypoglycemia when managing hyperglycemic patients with insulin and it is not known which of our two approaches will be better with respect to reducing hyperglycemia and hypoglycemia. Each patient will have a routine consultation by the Endocrinology Consult Service (ECS) or the Glucose Management Service (GMS) and will have blood glucose levels monitored at least daily by those services. If glucose levels are outside the target range of 80 – 180 mg/dL, insulin doses will be adjusted accordingly by those services. Cumulative data, including the frequency of hypoglycemia, will be reviewed by the Principal, Co-Principal and Fellow Investigators after the first 3 patients are entered into each group and then after every 5 patients in each group to determine if the basic algorithms (see Table) need to be adjusted.

WITHDRAWAL OF PARTICIPANTS:

Participants with be withdrawn from the study if their steroid regimen changes or stops from once a day dosing of methylprednisolone or prednisone.

RISKS TO PARTICIPANTS:

Risks: A confidentiality breach is a risk associated with data review research. As noted above, both hyperglycemia and hypoglycemia are inherent risks with inpatient glycemic management with insulin. Every effort will be made to reduce these by at least daily review of blood glucose levels on every participant with adjustments of insulin doses as needed.

There are no dangers to an embryo/fetus from insulin but we plan to exclude women known to be pregnant. Because there are no known dangers from insulin, we do not plan to do pregnancy tests, however.

POTENTIAL BENEFITS TO PARTICIPANTS:

Benefits: The participants are not likely to receive any benefit from the proposed research; however, society and investigators will benefit from the knowledge gained. As with all patients seen by the ECS and the GMS, patients will benefit from having their glucose levels monitored closely with frequent insulin adjustments made as needed.

VULNERABLE POPULATIONS:

No vulnerable populations will be included in this study

COMMUNITY-BASED PARTICIPATORY RESEARCH:

N/A

SHARING OF RESULTS WITH PARTICIPANTS:

Results of the study will not be directly shared with the participants.

SETTING:

All of the research including recruitment of patients and analyzing the data will take place at Northwestern Memorial Hospital

RESOURCES AVAILABLE:

The PI, Co-PI, ECS and GMS have extensive experience in managing blood glucose levels in inpatients at NMH and have published extensively on our experience.

Based on our previous experience, we anticipate that 2 –4 patients per week seen routinely by the ECS and GMS would be appropriate for this study and expect that at least 50% of patients will agree to participate.

The PI and Co-PI plan to devote about 5% of our time to supervising this research and the Fellow Investigator plans to devote 50% of her time to carrying out this research.

All patients will be seen at Northwestern Memorial Hospital. No special facilities are needed. Data analysis will be carried out using the computers and software available to the PI and Co-PI.

All participants will be followed individually by the Endocrinology Consult Service and Glucose Management Service and often will be seen by the hospital Diabetes Educator. These will provide additional medical and psychological support in addition to the Investigators in this study.

All members of the ECS and GMS will be informed about the nature of the study and instructed in how the study will be carried out. The Fellow-Investigator will liason directly with them each day on all participants in the study.

PRIOR APPROVALS:

N/A

RECRUITMENT METHODS:

- We will use patients primarily seen on the Endocrine Consult Service as well as the Glucose Management Service (GMS) who are on once daily dosing of prednisone or methylprednisone
- Consent will be obtained at the initial day of Endocrine or GMS inpatient consult, and then subsequently randomized.
- One group will receive NPH in addition to their current glargine lispro basal/bolus regimen with the addition of steroids. (See Table)
- Another group will continue to receive glargine and lispro; however, their basal and bolus regimens will be increased. (see Table)

NUMBER OF LOCAL PARTICIPANTS:

Proposed sample size : Our study aims to recruit 25 inpatients at Northwestern Memorial Hospital to each study arm for a total of 50 patients in the study.

PROVISIONS TO PROTECT THE PRIVACY INTERESTS OF PARTICIPANTS:

All glucose and demographic information will be stored on anonymized confidential files stored in firewalled FSM computers. A separate file will be kept with a patient number and any identifiable information and stored in the firewalled FSM computers.

Participants will be followed daily by the ECS or the GMS as well as the Fellow Investigator who will be able to address all questions and concerns,

The Research Staff will create a dataset in the Enterprise Data Warehouse so as to obtain access to any stored data on participants.

COMPENSATION FOR RESEARCH-RELATED INJURY:

N/A

ECONOMIC BURDEN TO PARTICIPANTS:

NONE

CONSENT PROCESS:

Consent will be obtained at the initial consult while the patient in inpatient at Northwestern Memorial Hospital. Consent with be obtain by the team members of the GMS or Endocrine Fellows on the ECS.

Adults Unable to Consent/ Cognitively Impaired Adults

Because the goal here is to improve glycemic control with less hyperglycemia and less hypoglycemia than standard methods, it seems reasonable to include adults who are cognitively impaired or who are unable to consent and who have appropriate individuals who can give appropriate assent. Such

appropriate individuals, in order of priority, would be those with durable power of attorney for health care, court appointed guardian for health care decisions, spouse, and adult child. Such assent will be documented on the Consent Form.

PROCESS TO DOCUMENT CONSENT IN WRITING:

Participants will be consented at the initial day of consult. A written document will be provided for signature. (see attached)

Table 1. Continue Standard Basal/Bolus Insulin* and add NPH in units adjusted for Prednisone doses according to the following table:

Prednisone Added (mg/day)	NPH Dose (U/mg Prednisone/day	Amount of total NPH added at top of range	Added total NPH Insulin (U/kg) for 70 kg person
> 80	No additional NPH	51	0.73
61-80	0.3	51	0.73
41-60	0.45	45	0.64
21-40	0.6	36	0.51
10-20	1.2	24	0.34

*Standard Basal/Bolus Insulin will be considered either a weight based dose (total daily dose of insulin 0.5 U/kg) or patient's home doses of insulin without adjustment

Table 2. Basal/Bolus Insulin adjusted for Prednisone doses according to the following table:

Prednisone Added (mg/day)	Glargine Dose (U/kg)	Breakfast Novolog Dose (U/kg)	Lunch Novolog Dose (U/kg)	Dinner Novolog Dose (U/kg)
>80	0.30	0.15	0.35	0.40
61-80	0.30	0.15	0.3	0.35
41-60	0.30	0.15	0.25	0.30
21-40	0.25	0.1	0.2	0.25
10-20	0.25	0.1	0.15	0.2
0*	0.25	0.08	0.08	0.08

*standard weight based dose of 0.5 U/kg divided 50/50 into basal (glargine) and prandial insulin divided into 3 premeal doses

Note: Prednisone and IV methylprednisolone will be judged to be equivalent with respect to addition of insulin doses according to above tables.

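### No rule keeps glucose readings taken before the first study dose out of the primary 3-day mean, and none are used as baseline; any loss of power is conditional

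*Combined protocol and SAP*

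**What the plan says.** Data and Specimen Management defines glycaemic control as "the mean of the 4 glucose levels (premeal and bedtime) for the first 3 days of treatment", with these means compared between the groups. That is up to 4 × 3 = 12 routine readings per patient. The same section adds the proportions of readings in two target ranges and the proportion below 70 mg/dL. No covariate is named, and no rule identifies the first eligible reading.

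On timing, Study Intervention says that one arm receives "NPH in addition to their current glargine lispro basal/bolus regimen at the time of the prednisone administration". The Background section describes high-dose steroids as usually given once daily in the morning. Table 2 sets glargine and three mealtime doses for the other arm; no clock time is given for glargine. Recruitment Methods states: "Consent will be obtained at the initial day of Endocrine or GMS inpatient consult, and then subsequently randomized". No hour is given, and Study Timelines says only that patients are followed for three days with the intervention.

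The sample-size paragraph assumes "a standard deviation of 30 mg/dL and assume half the difference in the means of about 30 mg/dL". It reports that "a sample size of 20 in each group" gives "statistical (two-tailed) power of 0.869" "using an alpha=0.05", and adds: "We plan to recruit 25 in each group to allow for drop-outs". The 30 mg/dL is roughly half of a 65 mg/dL difference (241 against 176) between 3-day means of premeal readings in a cited pilot study.

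**The concern.** A reading taken before the assigned regimen has started cannot reflect that regimen. Its expected difference between randomised arms is zero. Averaged into the outcome, it shrinks the estimated difference and adds variation between patients that treatment did not cause. The same reading has value as a baseline covariate, a use the plan does not make of it.

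The wording also leaves a choice open. Two analysts could reasonably compute different primary means from the same chart: one counting calendar days from the consult, the other counting from the first dose. In a trial of 50 patients that choice should not remain open once data are visible. It carries over to the in-target and below-70 mg/dL proportions, which rest on the same readings.

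**Working it through.** **1. Reproduce the plan's figure.** Inputs from the sample-size paragraph: difference 30 mg/dL, SD 30 mg/dL, n = 20 per arm, two-sided alpha 0.05. For a two-sample t-test, df = 2 × 20 − 2 = 38 and the noncentrality is 30 / (30 × √(2/20)) = 3.162. Power from the noncentral t is 0.869, which matches the plan.

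**2. Count the readings under each way of defining a day.**
- Calendar days: Day 1 holds pre-breakfast, pre-lunch, pre-dinner and bedtime. With NPH given alongside a morning steroid, and Table 2 mealtime insulin given after the premeal check (an assumption about practice), pre-breakfast comes before the first dose. A consult later that day puts further readings before it.
- Days counted from a morning first dose: pre-lunch, pre-dinner, bedtime and the next pre-breakfast, three times over. This is also 12 readings, all after the dose.

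The plan's wording fits both.

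**3. Power if 30 mg/dL is the difference after dosing.** Let k be the number of the 12 readings that carry no difference. The documents do not give k; 1 to 3 is an assumed range. The expected difference is 30 × (12 − k)/12, with SD held at 30.

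| k | Expected difference (mg/dL) | Power, 20 per arm | Power, 25 per arm (no drop-outs) |
|---|---|---|---|
| 0 | 30.0 | 0.869 | 0.934 |
| 1 | 27.5 | 0.806 | 0.888 |
| 2 | 25.0 | 0.728 | 0.823 |
| 3 | 22.5 | 0.637 | 0.738 |

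**4. Power if 30 mg/dL is the difference in the 3-day mean.** This is how the protocol derives it. Any dilution is then already inside the 30, and power stays at 0.869. Excluding k undifferentiated readings raises the expected difference to 30 × 12/(12 − k): 32.7 for k = 1 (power 0.919) and 36.0 for k = 2 (power 0.959), at 20 per arm with SD held at 30. Averaging 11 readings rather than 12 raises the SD of the mean by only about 0.2% to 1.1%, for an assumed equal correlation between readings of 0.6 down to 0.2.

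**5. Does the pilot carry the same dilution?** The documents do not say how it counted its first day. If its 9 readings (3 a day for 3 days) also held k pre-effect values, the matching 12-reading difference is 30 × [9/(9 − k)] × [(12 − k)/12]. That gives 30.9, 32.1 and 33.8 mg/dL for k = 1, 2 and 3, with power 0.888, 0.910 and 0.934.

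**The case against.** The strongest reply is that the plan ties the window to treatment, and nothing in it says that a pre-dose reading is counted. A window opened by the first dose holds 12 post-dose readings, as step 2 shows. Nor is the pre-breakfast reading certain to be untreated in both arms: if a patient in the Table 2 arm received study glargine or dinner insulin on the evening of the consult, the next pre-breakfast value would follow study insulin. This stands. Inclusion of pre-dose readings is possible under the text, not established by it.

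The second reply concerns power. A reader might infer from step 3 that the trial's true power is below 0.869. The documents do not support that. The 30 mg/dL comes from a difference in 3-day means, the same kind of quantity as the endpoint, and treating it as a post-dose effect is a further assumption. This also stands.

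The third reply is that opening each patient's window at the first dose of the assigned regimen could do harm. NPH waits for the steroid dose, whereas Table 2 insulin could begin at the next meal. After a late consult the arms might then contribute different mixes of times of day, and the Background reports steroid effects specifically before lunch and dinner. Dilution alone creates no false difference, but a start that depends on the arm could. This is right, and it determines the form of the fix.

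None of these replies supplies the missing rule.

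**Conclusion.** The gap holds in limited form. The plan has no rule that excludes readings before the first study dose from the primary mean, and it does not use them as baseline. On a calendar-day count at least one of 12 readings would be expected to be pre-treatment, and more after a later consult.

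Two stronger conclusions are not supported: that the outcome does contain such readings, and that power falls below the stated figure. The range 0.806 to 0.637 applies only if 30 mg/dL is a post-dose difference, 1 to 3 readings carry no difference, the difference is constant afterwards, and the SD stays at 30. On the protocol's own derivation, 0.869 stands.

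The case for a change does not depend on which reading is right. Under either, removing values that cannot differ by arm increases the expected difference, and a baseline covariate can improve precision. The size of that second gain depends on the correlation between baseline and outcome, which the documents do not give. The change should be made before analysis, but its absence does not invalidate the design.

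**What to change.** In Data and Specimen Management:

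- Open the 3-day outcome window by one rule that is the same in both arms and does not depend on the assigned regimen. One example is the first scheduled reading after the first once-daily steroid dose following randomisation, running for 12 scheduled readings. Twelve consecutive readings contain three of each type, wherever the window opens.
- Exclude earlier readings from the primary mean, from both in-target proportions and from the below-70 mg/dL proportion.
- Compare arms by ANCOVA, with the last routine glucose reading before randomisation as covariate. Taking it before randomisation ensures that study insulin in neither arm can affect it.
- State that the 30 mg/dL in the sample-size paragraph is the difference expected over this window.

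The cost is a few sentences. For some patients one or two early readings leave the outcome, possibly including some taken after Table 2 insulin has begun, or the window ends slightly later. It needs no fingersticks beyond the planned monitoring and no change to treatment.

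### Does the plan need a rule for analysing mean glucose by dosing-table version, given that the tables may be revised during the trial?

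*Combined protocol and SAP*

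**What the plan says.** The section on provisions to monitor the data for participants' safety sets out the reviews: "Cumulative data, including the frequency of hypoglycemia, will be reviewed by the Principal, Co-Principal and Fellow Investigators after the first 3 patients" in each group, "after every 5 patients in each group to determine if the basic algorithms (see Table) need to be adjusted". With 25 patients per group, the reviews fall at 3, 8, 13, 18 and 23 entered per group. The algorithms are Table 1 (NPH added to standard basal/bolus insulin) and Table 2 (adjusted basal/bolus insulin) at the end of the document. The same section provides for individual adjustment. When glucose leaves the target range of 80 to 180 mg/dL, "insulin doses will be adjusted accordingly by those services", meaning the consulting services.

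Procedures Involved describes a "randomized control study in which each patient will be randomized to one of two arms". Data and Specimen Management defines the primary measure as the mean of four daily values "for the first 3 days of treatment and comparing these means between the groups". It names no test, model, covariate or stratum. The privacy section mentions glucose and demographic files and a data warehouse dataset without a variable list. The document nowhere says that table revisions will be dated, that the version in force will be noted for each patient, or that version enters the analysis.

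**The concern.** Study Endpoints asks which of the two regimens controls glucose better. If a table changes partway through, the regimen in that arm is no longer the printed one, and a single pooled difference averages over versions. A reader could not tell which tables the result supports.

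There is also a possible loss of precision. If both tables change and glucose moves in both arms, the pooled comparison carries the between-version spread as extra within-arm variance. Under simple randomisation, the arms may also hold different shares of each version by chance. A version term would remove both effects when the shift is common to both arms. Finally, the investigators who see the cumulative data also decide on revisions, so leaving the choice between pooling and adjusting until afterwards means making it with data in view.

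**Working it through.** **Inputs from the documents.** SD 30 mg/dL, difference 30 mg/dL, two-sided alpha 0.05, 20 evaluable per group (power calculation in Data and Specimen Management). "We plan to recruit 25 in each group to allow for drop-outs", which implies 1 − 20/25 = 20% dropout.

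**Assumptions.** The documents give neither the size nor the timing of any shift in glucose after a revision. The method of randomisation is not stated either. Both are varied below.

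**1. The plan's own figure.** The plan states that "a sample size of 20 in each group would have statistical (two-tailed) power of 0.869". Noncentrality = 30 / (30 × √(2/20)) = 3.16. The noncentral t with 38 df gives 0.8690, so the figure reproduces.

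**2. Cost of a version term with arms balanced within versions.** Each extra version uses one degree of freedom: 37 df gives 0.8685 and 36 df gives 0.8680. The cost is about 0.0005 per version.

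**3. Same shift in both arms, versions balanced, change after 8 of 20 evaluable per arm.** The within-arm SD becomes √(30² + 0.4 × 0.6 × shift²). For a shift of 30 this is √(900 + 216) = 33.4. Simulated power:

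| Common shift (mg/dL) | Pooled | Version-adjusted |
|---|---|---|
| 5 | 0.869 | 0.870 |
| 10 | 0.863 | 0.869 |
| 15 | 0.855 | 0.868 |
| 20 | 0.844 | 0.869 |
| 30 | 0.811 | 0.868 |

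**4. The protocol's own trigger, without forced balance.** 50 patients, coin-toss randomisation, 20% dropout, one revision once both arms have 8 entered (simulation SE about 0.003):

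| Scenario | Pooled | Version-adjusted |
|---|---|---|
| Revision, no effect on glucose | 0.860 | 0.849 |
| Common shift 10 | 0.853 | 0.850 |
| Common shift 15 | 0.839 | 0.853 |
| Common shift 30 | 0.784 | 0.849 |
| One arm only, gap narrowed by 15 | 0.552 | 0.544 |
| Four revisions (3, 8, 13, 18), no effect | 0.860 | 0.822 |

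In the one-arm row, power falls because the true contrast is smaller after the revision. Adjustment does not recover it.

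**5. Chance imbalance of versions between arms.** The error this adds has mean 0. Its SD is 4.4 mg/dL for a common shift of 30 and 2.2 for a shift of 15. With blocks of 4 it is 2.1 for a shift of 30. It adds noise and no bias.

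**6. What by-version estimates could show.** SE = 30 × √(2/n): 24.5 mg/dL with 3 per arm, 15.0 with 8, 12.2 with 12. The target difference is 30, so even with 12 per arm the 95% half-width is about 1.96 × 12.2 = 24 mg/dL.

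**The case for a change.** The strongest case for a change is that the protocol itself schedules the decision to revise, so it should say what follows from a revision. A recorded version and a contingent sentence cost almost nothing before enrolment. Without a dated log, version might be hard to recover, because charted doses reflect individual adjustments as well as the tables. A prespecified rule would also remove discretion from investigators who have seen the data.

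Part of this stands. The plan is silent, a dated log is good practice, and a version-adjusted sensitivity analysis would be reasonable if a table did change. But the log changes no primary result, and a team that follows every participant daily can be expected to date a change to its own dosing table. Making the version term compulsory in the primary analysis is a trade-off: it gains with large common shifts, does nothing for small or one-arm shifts, and loses with several ineffective revisions. Nor does it settle the question of interpretation, since the adjusted estimate still averages over versions and the by-version estimates are too imprecise to separate them. The analysis text names no model, so it does not rule out a supporting adjusted analysis.

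**Conclusion.** The silence is real, but it is missing detail and not a fault in the design or analysis. If no table is revised, nothing is affected. If one is, concurrent randomisation keeps the pooled comparison valid for the strategies as delivered, which already include dose adjustment by the services. The stated power of 0.869 is correct.

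A material loss (about 0.06 in power, 0.811 against 0.868 or 0.784 against 0.849) requires both tables to be revised with similar effect and both arms to move by about 30 mg/dL, as large as the treatment difference the trial is powered to detect. Individual dose adjustment would tend to dampen such a shift. At 15 mg/dL the difference is about 0.01; at 10 it is under 0.01. In the other direction, the version term can cost 0.01 to 0.04 under simple randomisation. These figures rest on the plan's SD and difference, an average of 20 evaluable per arm, and assumed shift sizes and timing.

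Keeping the planned comparison as primary is sound. Dating any revision, and describing results by version should one occur, can be left to the trial team.

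### Home-insulin users start from different backgrounds in the two arms: the NPH arm may keep home doses, while Table 2 as written can cut them in the comparator

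*Combined protocol and SAP*

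**What the plan says.** The Study Intervention section describes both arms relative to what the patient already takes. For the NPH arm: "One group will receive NPH in addition to their current glargine lispro basal/bolus regimen at the time of the prednisone administration". For the comparator: "Another group will continue to receive glargine and lispro; however, their basal and bolus regimens will be increased". Recruitment Methods repeats both statements. The doses are in two tables at the end.

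- **Table 1 (NPH arm).** Standard basal/bolus insulin continues and NPH is added by steroid dose. The footnote defines the standard background as 0.5 U/kg/day or "patient's home doses of insulin without adjustment". No rule says which applies to whom, or that the choice precedes randomization.
- **Table 2 (comparator).** Glargine and three mealtime doses are listed in absolute U/kg for each steroid band. The only footnote belongs to the 0 mg row: "standard weight based dose of 0.5 U/kg divided 50/50 into basal (glargine) and prandial insulin divided into 3 premeal doses". There is no home-dose option, no floor at the current dose, and no instruction to read the entries as increments.

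The primary measure is the "mean of the 4 glucose levels (premeal and bedtime) for the first 3 days of treatment". The section on monitoring participant safety has the consult services review glucose at least daily and adjust insulin when values leave 80-180 mg/dL.

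**The concern.** The trial enrolls diabetic patients, and the Table 1 footnote itself anticipates home insulin. For those patients the tables do different things. One arm keeps the home regimen and adds to it; the other replaces it with a weight-based figure that may lie above or below it. Where it lies below, the comparator dose falls, against the protocol's own description of that arm.

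This matters for interpretation. The Background frames the open question as one of delivery: "the best way to administer this insulin is still unknown". It describes the pilot behind the power calculation as raising total insulin by 40% and giving that rise in two forms; for one group, "half of the arm received this increase in the form of NPH in addition to glargine and lispro". Here, in home-insulin users, the difference between arms in total and basal insulin also depends on the home dose and on which background is chosen. Randomization does not remove this, because it is part of the assigned regimen. A glargine cut in one arm can also act on the pre-breakfast value, one of the four daily readings in the primary mean.

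**Working it through.** **1. The plan's own figure.** Inputs from Data and Specimen Management: difference 30 mg/dL, SD 30 mg/dL, 20 per arm, two-sided alpha 0.05. Standard error = 30 × √(2/20) = 9.49; noncentrality = 30/9.49 = 3.16 on 38 degrees of freedom; power = 0.869. This reproduces the stated value, and nothing below changes it.

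**2. Totals by band.** The Table 2 total is glargine plus the three mealtime doses. NPH is Table 1's total at the top of the band (the >80 mg row keeps 51 U).

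| Prednisone (mg) | Table 2 total (U/kg) | Rise over 0 row | NPH (U) | NPH arm on 0.5 U/kg, 70 kg | Ratio NPH:comparator, 70 kg | Ratio, 100 kg |
|---|---|---|---|---|---|---|
| 0 | 0.25+0.08+0.08+0.08 = 0.49 | - | - | - | - | - |
| 10-20 | 0.25+0.10+0.15+0.20 = 0.70 | 0.21 | 24 | 0.84 | 1.20 | 1.06 |
| 21-40 | 0.25+0.10+0.20+0.25 = 0.80 | 0.31 | 36 | 1.01 | 1.27 | 1.08 |
| 41-60 | 0.30+0.15+0.25+0.30 = 1.00 | 0.51 | 45 | 1.14 | 1.14 | 0.95 |
| 61-80 | 0.30+0.15+0.30+0.35 = 1.10 | 0.61 | 51 | 1.23 | 1.12 | 0.92 |
| >80 | 0.30+0.15+0.35+0.40 = 1.20 | 0.71 | 51 | 1.23 | 1.02 | 0.84 |

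NPH is set in units per mg of steroid and Table 2 in U/kg, so the ratio varies with weight and steroid dose even on a common background. There is no single planned ratio.

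**3. When Table 2 cuts.** With home total H and band total T, the comparator's change is T/H − 1, which is negative when H > T. Glargine falls when home glargine exceeds 0.25 U/kg at 10-40 mg (17.5 U at 70 kg) or 0.30 U/kg above 40 mg (21 U).

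**4. Worked example.** 70 kg, newly started prednisone 20 mg, NPH 24/70 = 0.343 U/kg, T = 0.70. The home doses are assumptions.

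| Home dose H (U/kg) | NPH arm, H + 0.343 | Comparator | Comparator change from home | Gap (U/kg) |
|---|---|---|---|---|
| 0.3 | 0.64 | 0.70 | +133% | −0.06 |
| 0.5 | 0.84 | 0.70 | +40% | +0.14 |
| 0.7 | 1.04 | 0.70 | 0% | +0.34 |
| 0.9 | 1.24 | 0.70 | −22% | +0.54 |

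The gap changes sign at H = 0.70 − 0.343 = 0.357 U/kg. If home insulin of 0.9 U/kg is split 50/50, glargine stays at 0.45 U/kg in the NPH arm and drops to 0.25 in the comparator (0.25/0.45 − 1 = −44%).

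At 40 mg with an assumed home dose of 1.0 U/kg, the NPH arm gets 1.0 + 36/70 = 1.51 U/kg and the comparator 0.80 (−20%). Above 40 mg, a cut in the total needs a home dose over 1.00, 1.10 or 1.20 U/kg, depending on the band.

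**5. The wording about basal insulin.** Table 2 glargine is 0.25 U/kg in the 0, 10-20 and 21-40 mg rows. Even on the 0.5 U/kg background, basal insulin does not rise until the dose exceeds 40 mg.

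**The case against.** The fairest defence is that the prose starts both arms from the current regimen, that the tables are called basic algorithms, and that specialist services apply and adjust them. On that view the Table 1 footnote means home doses for those who have them and 0.5 U/kg for the rest, and Table 2 was written with the latter in mind. This stands in part: the documents do not show that any patient's insulin will in fact be cut. But they do not limit Table 2 to patients without home insulin, and if it were so limited, comparator patients on home insulin would have no protocol dose.

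Daily adjustment softens the problem. It follows out-of-range readings, though, and the endpoint covers only three days: with one review a day, up to 4 of the 12 values can precede the first correction.

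It is also fair to say that the stated aim is to compare regimens, and that the trial is not dose-matched even on a common background. A glucose difference produced by the assigned doses is therefore a real effect of those regimens. A reader might infer an inflated false-positive rate, or a bias of so many mg/dL in favour of NPH. Neither follows. The difficulty is attribution to NPH, not type I error. The share of patients on home insulin, their doses and the glucose response are not given, and the gap reverses at low home doses.

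A reader might also infer underdosing from the Background's cited conclusion that "insulin doses should be increased by at least 30% when the corticosteroid therapy is started". That study was in type 1 patients on pumps, and the protocol does not adopt its figure as a dosing target.

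**Conclusion.** The point holds as a defect in the dosing rules. For home-insulin users, the NPH arm may keep the home dose and add to it, while Table 2 read literally replaces it and cuts any total above 0.70 to 1.20 U/kg, depending on the band. That contradicts the text on the comparator. In the 0.9 U/kg example the arms differ by 0.54 U/kg instead of 0.14 on the 0.5 U/kg background, so adding NPH cannot be separated from keeping versus cutting home insulin.

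The size rests on assumed home doses at one weight and one steroid dose. It is largest in the low steroid bands and may concern few patients. Patients without home insulin, and those on the 0.5 U/kg background in both arms, are not affected by this asymmetry. No figure for bias in mg/dL or for error rates is warranted. The change should be made because the rule conflicts with the text and is simple to correct.

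**What to change.** Use one background rule for both arms: for example, home doses for patients on home insulin and 0.5 U/kg otherwise, recorded before randomization. In the comparator, add Table 2's rise over its 0 row to that background:

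| Prednisone (mg) | Glargine | Breakfast | Lunch | Dinner | Total rise (U/kg) |
|---|---|---|---|---|---|
| 10-20 | 0 | 0.02 | 0.07 | 0.12 | 0.21 |
| 21-40 | 0 | 0.02 | 0.12 | 0.17 | 0.31 |
| 41-60 | 0.05 | 0.07 | 0.17 | 0.22 | 0.51 |
| 61-80 | 0.05 | 0.07 | 0.22 | 0.27 | 0.61 |
| >80 | 0.05 | 0.07 | 0.27 | 0.32 | 0.71 |

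The contrast then no longer depends on the home dose. At 20 mg it is +0.34 versus +0.21 U/kg at 70 kg, and +0.24 versus +0.21 at 100 kg. Because the rise at 10-40 mg is entirely prandial, Study Intervention and Recruitment Methods should stop saying that basal doses also go up in those bands.

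The alternative is to remove the home-dose option, so that both arms start from 0.5 U/kg.

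The administrative cost is edits to the tables and text plus, for the first option, one recorded field; no extra patients or visits. The clinical cost is real. At 20 mg, a comparator patient with a home dose of 0.9 U/kg would start at 0.9 + 0.21 = 1.11 U/kg instead of 0.70, with more hypoglycemia risk. One at 0.3 U/kg would start at 0.51 instead of 0.70 and may run higher until adjusted. The alternative avoids both but cuts high home doses in both arms.
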